#### Introduction

Psychological intervention is an evidence-based treatment option for patients with non-anorexic eating disorders (ED). Cognitive Behavioral Therapy (CBT) has proven effectiveness for treating a broad spectrum of ED diagnoses. For instance, CBT for Bulimia Nervosa (CBT-BN) is acceptable to service-users with 80 to 85% completion rates and effectiveness in reducing core features of BN and improving comorbid psychological problems (Fairburn, 1997; Fairburn et al., 1993; Anderson, 2001; Murphy et al., 2010). Gains on primary outcomes are also mostly maintained at long term follow-up (Fairburn et al., 1995, Wilson et al., 2002).

More recently, attention has been paid to transdiagnostic aspects of psychopathology, present across all ED diagnoses. Elements such as clinical perfectionism, low self-esteem, Intolerance of Emotions and underlying interpersonal Difficulties all have potential to impact on the maintenance of gains and are also risk factors for ED relapse if unaddressed in psychotherapy.

In particular, maladaptive perfectionism is considered to be a core transdiagnostic feature of ED (Halmi et al., 1977; Bruch, 1973; Garner, 1986; Bauer & Anderson, 1989; Casper, 1983; Davis, 1997; Davis, et al., 2000) and a precipitant risk factor in the development of ED (Bastiani et al., 1995; McLaren et al., 2001; Ruggiero et al., 2003; Vitousek & Hollon, 1990). In addition, numerous studies have identified low self-esteem as a risk factor for developing EDs and a maintain factor (Button et al., 1997; Button et al., 1996; Canals et al., 1996; Geller et al., 2000; Ghaderi & Scott, 2001; Lilenfeld et al., 1998; Neumark-Sztainer & Hannan, 2000; Rastam, 1992; Wichstrom, 1995; Fairburn et al., 1997; Fairburn et al., 1998; Fairburn et al., 1999). Patients with low self-esteem endorse a generalized negative self-concept, above and beyond their inability to control their eating patterns, body image and weight. For example, as a function of low self-esteem patients may have low confidence in their ability to effectively maintain changes in their eating habits (Fairburn et al., 2002).

Intolerance of Emotions has been identified as a potentially transdiagnostic factor, albeit in a subgroup of patient with EDs (Meyer et al., 1998; Steinberg et al., 1990; Stice, 1994; Waller, 2002). These individuals present with difficulties in effectively coping with emotional states, both negative and positive. Emotion regulation is often arrived at via dysfunctional strategies such as self-harm or alcohol and substance misuse (Claes et al., 2001; Holderness et al., 1994; Paul et al., 2002).

Finally, with regard to Interpersonal Difficulties studies have shown that a dysfunctional family environment is associated with a higher risk of continuing with restrictive eating behaviors, particularly in younger patients, intensifying a need for a perceived sense of "control". Examples are dysfunctional food-related activities such as controlling food intake and calories, as a response to a perceived hostile interpersonal environment (Fairburn et al., 1999). Bulimia nervosa has also been associated with interpersonal sensitivity in social interactions, further associated with self-criticism and lowered mood (Steiger et al., 1999). In general, poor interpersonal functioning has also been

identified as a predictor of poorer treatment response (Agras et al., 2000a; Steiger, Leung, & Thibaudeau, 1993).

Given the importance of transdiagnostic elements, an enhanced form of CBT was developed, adding a therapeutic focus on these maintenance factors (CBT-E; Fairburn, 2008) to CBT-focused (CBT-f, Fairburn et al, 2003) which originally included psycho-education, nutritional re-education and overall clinical management for ED.

CBT-E has demonstrated acceptability and effectiveness for all forms of EDs (Cooper & Fairburn, 2011; Fairborn et al., 2003) including anorexia nervosa (Dalle Grave et al., 2013a; Dalle Grave et al., 2013b; Dalle Grave et al., 2014; Fairburn et al., 2013; Zipfel et al. 2014), bulimia nervosa (Poulsen et al., 2014; Wonderlich et al., 2014), and intransdiagnostic samples (Fairburn et al. 2009) both in adults (Fairburn et al, 2009; Fairburn et al, 2013) and in younger patients (Dalle Grave et al, 2013). In a direct comparison with interpersonal psychotherapy for adults (IPT), CBT-E was found to be more effective (Fairburn et al, 2015) in patients with EDs.

However, there remain challenges with implementing CBT-E (Fairburn et al. 2014; Le Grange et al., 2020; Frostad et al., 2018; 2021). First, dropout rates remain significant, affecting at least /4 of patients, even in high quality trials (Linardon, et al., 2018).

Second, remission rates are also a cause for concern. For instance, Poulsen and colleagues (2014) reported that in a sample of patients with BN, after 5 months, only CBT-E 36% of patients remitted, although this was favorable compared to psychoanalytic psychotherapy (23.5% remitted; (Poulsen et al., 2014). Other studies suggest that approximately 37% of patients who received CBT-E were remitted at post-treatment, which increased to 50% at 4-month follow-up (Wonderlich et al., 2014). Another study highlighted that 55% of CBT-E treatment completers met criteria for remission at post-treatment (Allen et al., 2012).

Third, CBT-E in transdiagnostic samples appears to result in moderate to large decreases in binge eating behavior and small to moderate decreases in purging behaviors. For instance, for patients with BN, CBT-E resulted in cessation of bingeing and purging for 22.5% (Wonderlich et al., 2014), 42% (Poulsen et al., 2014), and 44% to 40% (for CBT- f and CBT-E, respectively, using completer data; Thompson-Brenner et al., 2016) of patients at post treatment. Rates were generally well maintained up to 19-month follow-up.

Finally, most studies have focused on eating behavior as the main outcome, while other elements such as social & interpersonal functioning and other comorbid symptom disorders have been less frequently investigated. Those outcomes have important implications for both relapse prevention and functional recovery, as many patients who have registered improved eating-related outcomes through treatment may still experience difficulties in quality of life and interpersonal relationships.

Linked to this, several transdiagnostic elements that may contribute to ED psychopathology are potentially underspecified in CBT-E. One transdiagnostic element is poor metacognition (Semerari et al., 2003), denoting the capacity to make sense of mental states and use mentalistic knowledge to deal with suffering and interpersonal problems and the second are maladaptive interpersonal schemas about self and others. Recent evidence suggests metacognitive difficulties are present in ED. For instance, Aloi and colleagues (2020; 2021) reported poor awareness of emotions and poor emotion regulation in patients with binge eating disorder. Further, Monteleone et al. (2020) reported difficulties in overall mentalizing capacities as well as impaired empathy in ED diagnosed patients, and that these were also correlated with ED symptoms. A further element of metacognition, reduced awareness of one's own affects (commonly known as alexithymia), with meta-analytic evidence (Westwood et al., 2017) that reduced capacity to identify own emotions and communicate them to others is present in all ED types. Overall, evidence supports the proposition that poor capacity to

recognize and reflect upon the mental states of the self and of the others is impaired across ED populations and this is in turn connected with poor emotion regulation and eating disorder symptoms. Therefore, interventions that increase metacognitive capacity may in turn lead to reductions in ED symptoms.

There are also significant associations between cognition, maladaptive patterns and dysfunctional eating behavior (Fairburn, 2008). In this regard, patients with EDs demonstrate negative individual patterns relating to the self, the world and others, alongside as autobiographical memories based characterized by paternal emotional inhibition and social isolation (Basile et al., 2020). From a therapeutic perspective, restructuring these interpersonal schemas is required to reduce ED severity and to improve therapeutic alliance (Gilbert & Leahy, 2009). For instance, Maher et al's (2022) review of 29 studies suggests that individuals with an ED diagnosis or high level of ED symptomology reported higher scores across all early maladaptive schemas (EMS) subscales. In particular, Unrelenting Standards were pervasive across all ED diagnoses. Insufficient Self-control was associated with binge eating and purging behaviors. Social Isolation, Social Undesirability and Emotional Inhibition were also common across ED diagnoses (Maher et al., 2022). It has also been suggested that there is a mediating relationship between EMS, and multidimensional perfectionism, specifically in relation to body image concern in EDs (Boone et al., 2012). Finally, experiences of childhood trauma have also been associated with more severe ED symptoms, further linked to "disconnection and rejection" (Meneguzzo et al., 2021).

Given the current status of CBT-E, and the potential for targeting transdiagnostic factors such as metacognition and interpersonal schemas as mechanisms of change in ED, we propose that Metacognitive Interpersonal Therapy (MIT; Dimaggio et al., 2007; 2015; 2020) is a candidate intervention to enhance treatment adherence and improve outcomes, particularly for those who have either struggled to engage with or not responded to CBT-E.

MIT (Dimaggio et al., 2007; 2015; 2020) is focused on a fine-grained understanding of personality pathology, incorporating consideration of metacognitive difficulties and maladaptive interpersonal schemas. Therefore, it could be combined with CBT-F to form a comprehensive approach to targeting ED pathology, both at the level of eating behavior and personality. MIT is an empirically supported intervention, with evidence for its effectiveness for personality disorders and other complex mental health conditions, across multiple settings and geographies (Dimaggio et al., 2017; Gordon-King et al., 2018; Inchausti et al., 2018; 2020; Popolo et al., 2018; 2021; Pasetto et al. 2021, Simonsen et al., 2022).

### Method/Design

### 2.1 Aims and hypotheses

The study is a pilot randomized controlled trial that aims to evaluate the feasibility and effectiveness of weekly MIT in addiction to CBT-F in a group of adults diagnosed with ED. Specifically, we will investigate in a sample of non-underweight adults presenting with ED whether once compared to CBT-E, a treatment combining MIT and CBT-F is a) feasible, b) well-tolerated and c) potentially effective on eating disorders symptoms and other outcomes. The study is defined according to the Standard Protocol Items: Recommendations for Interventional Trials (SPIRIT) statement and guidelines (Chan et al., 2013).

### 2.2 Study design

A parallel-group randomized controlled trial design will be used in order to compare CBT-E (n = 10) condition to combined MIT/CBT-F (n = 10). Patients in both conditions will receive 20 weekly sessions of either CBT-E or MIT/CBT-F.

Primary outcomes will be represented by ED and comorbid symptoms as assessed with the Eating Disorder Examination Questionnaire (EDE-Q6) (Fairburn & Beglin, 1994), which are expected to be

reduced after treatment. Other measures of ED and comorbid symptoms will still be considered primary outcomes. Secondary outcomes are anxiety, depression and global psychological symptoms. Lastly, exploratory outcomes will be difficulties in the emotional sphere such as understanding, processing, regulating or describing emotions.

Predictors, mediators and outcome variables will be measured at baseline, after 10 sessions with the exclusion of SCID-5 Interview, at the end of the treatment, and in the following 3, 6, 12, 18 and 24 months after the treatment. Two psychotherapies for each arm will be randomly selected, audio recorded and later analysed in order to explore the therapy process.

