#### 2.4 Participants

Twenty consecutive participants will be recruited at the CTI Disturbi Alimentari e Obesità. All participants will be aged 18 years or over and treatment-naive. They will be screened for a main diagnosis of ED in the past 6 months. Inclusion and exclusion criteria are reported in Table 1.

Inclusion Criteria	Exclusion Criteria
Aged >18 years	Acute psychotic episode, psychotic symptoms, Bipolar I disorder; antisocial personality disorder
ED diagnosed in the past 6 months	Suicidal ideation
Seeking treatment for eating disorder	Substance abuse
Able to provide written, informed consent	Previous psychological intervention for other eating disorders
BMI > 18.5	Currently involved in other ongoing treatment

Table1 Inclusion and Exclusion Criteria

All participants meeting inclusion criteria will be informed about the trial and will decide whether to take part. A regular ED-focused treatment will be offered to all participants excluded from the trial or who decline participating. All participants will give written informed consent before participation.

Drop-out rates from each arm will be reported for patients withdrawing during treatment and those lost to follow-up. Treatment is delivered in a private center therefore participants are paying for their care, however there is no financial incentive to participate in the trial. The study protocol is written in accordance with the European Union Standards of good clinical practice and in accordance with the Declaration of Helsinki. The protocol has been approved by the Ethics Committee of the Department of Dynamic and Clinical Psychology of "La Sapienza" University (Rome) Prot. n. 0000781, 05/13/2022 - [UOR: SI000092 - Classif. VII/15]

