All the psychometric tests will be administered at baseline, after 10 sessions (with the exclusion of SCID-5 Interview which will be only administered...), at the end of the treatment and in the following 3, 6, 12, 18 and 24 months after the treatment. The WAI will be administered monthly. All measures will be carried out by the research assistant who will be trained and weekly supervised.

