## 2.7 Procedure

Treatment-seeking participants at the CTI Disturbi Alimentari e Obesità will first receive an assessment screening visit. Once evaluated for inclusion/exclusion criteria, they will be informed about the study. If they wish to participate, they will be required to give written informed consent.

Tab.1. Flow chart of the study design

The researcher will ensure that the person is fully informed of the randomization process and their chances of receiving additional MIT sessions. Once informed and written consent has been obtained, baseline measures about primary and secondary outcomes will be completed.

Participants will then be randomized into two experimental conditions: CBT-F+MIT (experimental treatment) and CBT-E (standard treatment). All participants in each experimental condition will first receive two initial standard sessions mainly focused on investigating the compliance to the treatment and on understanding the maintenance factors of the ED.

**2.7.1. Experimental Treatment:** Participants in the CBT-F+MIT condition will receive a total of 20 sessions over 20 weeks. Specifically, 2 sessions will be based on CBT-F as usual only. During these sessions participants will receive psychoeducational training on eating behaviors and an introduction to the protocol tools, namely the monitoring form, weight chart, transdiagnostic formulation and Eating Problem Check List (EPCL).

These elements will be used at the beginning of the remaining 18 sessions, in order to monitor the regulations of eating behaviors as well eliciting narrative episodes. These materials will form the basis for the MIT-part of the session, in which therapists will seek to form with the patient a shared understanding of the psychological reasons underlying their ED symptoms and their maladaptive interpersonal functioning. Once a shared understanding is reached, patients and therapist will work to develop healthier strategies for managing negative thoughts and feelings antecedent to disordered eating. They will also develop new strategies for engaging in social interactions that meet their

relational basic wishes, such as attachment, personal worth, autonomy and group belonging (Dimaggio et al., 2015; 2020).

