With MIT therapy, patients will be guided in to understand that perfectionism and the need for control they experience through ED are coping strategies developed within interpersonal patterns of interaction with significant others, where low self-esteem and emotive dysregulation play a central role.

Overall, MIT aims to improve individuals' capacity to make sense of their own affect and cognitions and become aware of being driven by maladaptive, rigid and biased schemas about self and others. This enables the individual to form a richer understanding of the mind of the others and use this knowledge to react in more adaptive ways to social difficulties or evolutionary selected wishes (such as being cared of, finding a satisfying place in the social hierarchy, explore the environment and be autonomous). MIT also enables individuals to reflect on how these schemas may act as triggers for disordered eating behavior and develop more effective coping strategies in face of interpersonal stressors.

MIT sessions will be integrated within the CBT-F protocol (Fairburn; 2003) which will provide psycho-educational, nutritional re-education and management for ED. In particular, CBT aims to inform patients about the importance of self-control, the dangers of some restrictive behaviors such as self-induced vomiting. Moreover, CBT provides strategies to patients in order to monitor their usually dysfunctional behaviors and so increasing their awareness (i.e., food diary method) while reducing the availability of food and encourages activities that are incompatible with overeating. Patients will be trained in problem solving in order to change these feelings, as well as in increasing their self-awareness in order to recognize irrational thoughts about their body weight and shape. Additionally, they will be gradually exposed to foods that they had been avoiding [20].

**2.7.2 Standard Treatment:** participants in the CBT-E condition will receive a total of 20 CBT-E sessions over 20 weeks. This will include the standard CBT-E protocol outlined above, without the additional MIT elements.

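### Outcome visits are timed by therapy sessions and end of treatment, so patients who stop early have no clear assessment schedule for the planned ITT analysis

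*Combined protocol and SAP*

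**What the plan says.** Section 2.2 sets the schedule: outcomes are "measured at baseline, after 10 sessions with the exclusion of SCID-5 Interview, at the end of the treatment", and then at five follow-ups. Section 2.5 repeats it, placing the later assessments "at the end of the treatment and in the following 3, 6, 12, 18 and 24 months after the treatment". The only measure on a calendar interval is the alliance inventory, given monthly.

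The planned course is the same in both arms. Section 2.2 states: "Patients in both conditions will receive 20 weekly sessions of either CBT-E or MIT/CBT-F". Sections 2.7.1 and 2.7.2 both give 20 sessions over 20 weeks.

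On patients who leave, section 2.4 says: "Drop-out rates from each arm will be reported for patients withdrawing during treatment and those lost to follow-up". It does not say whether or when they are assessed.

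Section 3 plans ITT and per-protocol analyses with an exploratory repeated-measures model of effects over time. It also treats the number of sessions received as something that varies, to be explored as a moderator.

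**The concern.** An ITT analysis needs outcomes from randomised patients whether or not they complete therapy. Here the trigger for measurement is itself a therapy event. Followed literally, it makes the mid-treatment visit conditional on attending ten sessions, and it ties every later visit to an endpoint that has two possible dates for a patient who stops.

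Attendance and dropout are also how section 4 judges tolerability, so whether and when a patient is measured depends on something the trial expects treatment to influence. The research assistant who gives all the measures has no written rule for a patient who has stopped, and two such patients could be handled differently. The lead primary outcome, the EDE-Q6, is collected at these visits. An assessment that was never made, or was made at an arbitrary time, cannot be repaired at analysis.

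**Working it through.** The plan states no figure to reproduce. The check is a reading of the schedule, followed by a count of what it affects.

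**Patients who attend weekly and finish.** Twenty weekly sessions put session 10 at about week 10 and the end at about week 20. Their visits align and there is no problem.

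**Patients who stop after session s, with s below 20.**
- Mid visit: triggered only if s is at least 10.
- End visit: week s if treatment ends when therapy stops, week 20 if the planned end is meant. The two readings differ by 20 − s weeks. For illustration, a stop after session 5 gives week 5 or week 20, a gap of 15 weeks.
- The five follow-ups inherit the same gap.

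**Patients who miss weeks but continue.** Twenty sessions in 20 weeks leave no slack. Each missed week that is made up moves the later session-based visits by one week. The documents give no attendance rate, so this is not sized.

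**How many patients stop early.** Rates given in the documents:
- Section 4: 10–15% expected with CBT-F+MIT (written as an upper bound), and a cited average of 17.51%.
- Introduction: at least one quarter for CBT-E. The 80–85% completion of CBT-BN implies 15–20%; neither arm receives that treatment, but the figure lies inside the range.

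Applied to all 20 patients:
- 20 × 0.10 = 2
- 20 × 0.15 = 3
- 20 × 0.1751 = 3.5
- 20 × 0.25 = 5

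By arm, 10 × 0.10 + 10 × 0.1751 = 2.75 and 10 × 0.15 + 10 × 0.25 = 4.0, which lie within 2 to 5. With independent patients and one common rate, the chance of at least one early stopper, 1 − (1 − rate)^20, is 0.878 at 10% and 0.997 at 25%.

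**How many visits.** Post-baseline visits per patient: 1 mid + 1 end + 5 follow-ups = 7, so 20 × 7 = 140.
- Mid visit never triggered: 0 if every early stopper reaches session 10, up to 5 if five patients stop and all do so before it. That is 0 to 5 of 140 (0–3.6%).
- Later visits with ambiguous timing: 2 × 6 = 12 to 5 × 6 = 30 of 140 (8.6–21.4%).
- With the by-arm counts: 2.75 × 6 = 16.5 to 4.0 × 6 = 24 (11.8–17.1%).

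**The case against.** The strongest reply is that end of treatment is not undefined. Two ordinary readings supply a date, and under either one the follow-ups can be scheduled. That stands. A reader might add the two counts at the upper end, 5 + 30 = 35 of 140, and conclude that 25% of visits have no date or trigger. The documents do not support this. Only the mid visit can lack a trigger; the other six are ambiguous between two dates. The 25% is also just the 5-in-20 dropout rate restated, and it requires every dropout to leave before session 10. What remains is that the plan does not choose between the readings, and the choice moves a visit by up to the whole unfinished part of the course.

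A reader might also infer an offset between arms from section 2.7, where "All participants in each experimental condition will first receive two initial standard sessions", by supposing that these are additional to the 20 in one arm only. Nothing supports that. Section 2.7.1 says patients "will receive a total of 20 sessions over 20 weeks", made up of 2 sessions and then "These elements will be used at the beginning of the remaining 18 sessions"; section 2.7.2 says "participants in the CBT-E condition will receive a total of 20 CBT-E sessions over 20 weeks"; and the initial sessions are given to everyone.

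Timing the mid visit by sessions is a defensible choice for mediator and process questions, since it compares patients at equal exposure. That also stands, and it is a cost of the change.

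Finally, the stakes are limited. This is a 20-patient pilot, its analyses are largely descriptive, and a mixed model keeps patients with missed visits if data are missing at random. A schedule could also appear in the unreadable figure in section 2.5 or flow chart in section 2.7, or contact after withdrawal could be covered in consent material that was not available. These points lower the priority but do not supply the rule.

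**Conclusion.** The point holds as a cheap improvement worth making. On the readable text, assessment depends on attendance: patients who stop before session 10 never trigger the mid visit, and the later visits of every early stopper have ambiguous timing since randomisation, although ITT repeated-measures analyses are planned. About 2 to 5 of 20 patients are affected, with 0 to 5 of 140 post-baseline visits untriggered and about 12 to 30 ambiguous.

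The size rests on applying the cited dropout rates to this sample. Neither end is a hard limit, because the expected rate is given as an upper bound and the CBT-E rate as a minimum. The counts are visits without a clear rule, not visits known to be missing. It would go too far to say that the comparison is biased: unequal timing or unequal loss between arms is possible, but the documents do not show it.

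**What to change.** In sections 2.2 and 2.5, state that every randomised patient is asked to complete the outcome measures at the nominal times of the planned 20-week course, whether or not still in therapy: about week 10, about week 20, and 3, 6, 12, 18 and 24 months after the planned end. Count from the same origin in both arms. Record the number of sessions attended by each visit, so that the mediator and sessions-received analyses can still account for exposure, and record the reason for any missed visit. In section 3, name scheduled visit as the time variable of the ITT model. Any visit window should be chosen on practical grounds; the four-week recall period of the EDE-Q6 does not determine its width.

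The change is to protocol wording, with the same visits, questionnaires and research assistant. It has three costs:
- Mid-course values no longer reflect equal session exposure by design.
- Some late finishers are assessed while still in therapy.
- Patients who have stopped must be contacted for about two years after the planned end. Some will decline, particularly as they left a private centre where they paid for care, and their data will stay missing.
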